## 5.2.2 Subject Disposition

The number (percentage) of subjects who screened for participation, discontinued study drug and discontinued from the study will be summarized, along with the primary reason for screening failure and/or discontinuation.

Listings of all subjects screened for participation, discontinued study drug and discontinued from the study, including primary reasons for screening failure and/or discontinuation will be provided.

## 5.2.3 Protocol Deviations

All major protocol deviations will be determined prior to database lock and will be agreed upon by a review of individual subject data. The summary table and listing of major protocol deviations will be provided using data in the clinical database.

## 5.2.4 Demographic and Other Baseline Characteristics

Demographic and other baseline characteristics for the FAS will be summarized using descriptive statistics. They include:

- age (years) and age group (<65 years, >=65 years)
- sex (male, female)
- race (White, Black or African American, Asian [Japanese, Chinese, Other Asian], American Indian or Alaska Native, Native Hawaiian or other Pacific Islander, and Other)
- ethnicity (Hispanic or Latino, not Hispanic or Latino)
- height (cm)
- weight (kg)
- ECOG performance status.

The number (percentage) of subjects of previous anti-cancer medications, previous radiotherapy and tumor diagnosis assessed in the baseline for the FAS will be summarized, respectively.

Listings of demographics, tumor diagnosis, Child-Pugh classification, previous anti-cancer medications and previous radiotherapy will be provided.

## Medical history

The number (percentage) of subjects reporting a history of any medical condition will be summarized for the FAS. The medical history and current medical condition at baseline will be summarized as appropriate. Reported medical conditions will be coded using Medical Dictionary for Regulatory Activities (MedDRA), version 19.0 or later.

A listing of medical and surgical history will be provided.

### 5.2.5 Prior and Concomitant Therapy

All investigator terms for medications recorded on the case report form (CRF) will be coded using the World Health Organization Drug Dictionary (WHO DD) 2016 or current. The number (percent) of subjects who have taken prior and concomitant medications will be summarized on the FAS by Anatomical Therapeutic Chemical (ATC) Classification and WHO DD preferred term. Prior medications will be defined as medications that stopped prior to the first dose of study drug. Concomitant medications will be defined as medications that started after the date of the first dose of study drug up to 30 days after the subject's last dose.

All medications will be presented in subject data listings.

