14. Females of childbearing potential should avoid becoming pregnant and use highly effective contraception while on treatment and for at least 1 month after finishing treatment. Females of childbearing potential must not have had unprotected sexual intercourse within 30 days before study entry and must agree to use a highly effective method of contraception (eg, sexual abstinence, an intrauterine device, a contraceptive implant, an oral contraceptive, or have a vasectomized partner with confirmed azoospermia) throughout the entire study period and for 30 days after study drug discontinuation. Sexual abstinence is considered a highly effective method only if defined as refraining from heterosexual intercourse during the entire period of risk associated with the study treatment. The reliability of sexual abstinence needs to be evaluated in relation to the duration of the clinical study and the preferred and usual lifestyle of the subject. Periodic abstinence (calendar, symptothermal, and post-ovulation methods), withdrawal (coitus interruptus), spermicides only, and lactational amenorrhea method are not acceptable methods of contraception. Female condom and male condom should not be used together. Females who are using hormonal contraceptives must have been on a stable dose of the same hormonal contraceptive product for at least 4 weeks before dosing and must continue to use the same contraceptive during the study and for 30 days after study drug discontinuation. Women using oral hormonal contraceptives should add a barrier method.

15. Be willing and able to comply with all aspects of the protocol.

16. Provide written informed consent prior to any study-specific Screening procedures.

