9.3.2 Exclusion Criteria

Subjects who meet any of the following criteria will be excluded from this study:

1. Other malignancy active within the previous 2 years except for basal or squamous cell skin cancer, stage 1 prostate cancer, superficial bladder cancer, or carcinoma in situ of the cervix or breast that has completed curative therapy.
2. Current evidence of corneal disorder/keratopathy including but not limited to corneal epithelial thinning, bullous/band keratopathy, corneal abrasion, inflammation/ulceration, or keratoconjunctivitis (to be confirmed by ophthalmological examination). Pre-existing cataract is not a reason for exclusion.
3. Brain or subdural metastases are not eligible, unless they have completed local therapy and have discontinued the use of corticosteroids for this indication for at least 4 weeks before starting treatment in this study. Any signs (eg, radiologic) or symptoms of brain metastases must be stable for at least 4 weeks before starting study treatment.
4. Genetic diseases of the liver that may complicate review of safety data.
5. Known human immunodeficiency virus infection.
6. Uncontrolled significant active infections, except HBV or HCV. Subjects with HBV are eligible, but should be taking appropriate antiviral medication if indicated. Subjects with HCV are eligible but must not be taking any concomitant treatment for HCV while receiving H3B-6527.
7. Major surgery or other locoregional treatment within 4 weeks before the first dose of study drug or radionuclide treatment (eg, ⁹⁰Yttrium intra-arterial treatment) within 8 weeks before the first dose of drug administration.
8. Inability to take oral medication, or presence of malabsorption syndrome or any other uncontrolled gastrointestinal condition (eg, nausea, diarrhea, or vomiting) that might impair the bioavailability of H3B-6527. Subjects with prior gastric resection are eligible.
9. Use of any drug that is a strong inhibitor or inducer of the CYP3A4 enzyme or the P-glycoprotein transporter within at least 2 weeks before the start of study drug and during the conduct of the study unless there is an emergent or life-threatening medical condition that requires it.
10. Use of any drug known to prolong corrected QT (QTc) interval within at least 2 weeks before the start of the study drug and during the conduct of the study.

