9.4.8 Prior and Concomitant Therapy

Any medication (including over-the-counter medications) or therapy administered to the subject during the study (starting at the date of informed consent) will be recorded on the Prior & Concomitant Medication Case Report Form (CRF) or Non-Pharmacological

Procedures CRF. The investigator will record on the Adverse Event CRF any AE for which the concomitant medication/therapy was administered.

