9.7.1.5 Prior and Concomitant Therapy

All investigator terms for medications recorded in the CRF will be coded to an 11-digit code using the current version of the WHO Drug Dictionary. The number (percentage) of subjects who took prior and concomitant medications will be summarized on the Full Analysis Set by study part and cohort and overall, Anatomical Therapeutic Chemical class (ie, anatomical class, therapeutic class, pharmacologic class, chemical class), and WHO Drug Dictionary preferred term (PT). Prior medications will be defined as medications that stopped before the first dose of study drug. Concomitant medications will be defined as medications that started after the date of the first dose of study drug up to 30 days after the subject's last dose. All medications will be presented in subject data listings.

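### Minor, but wrong as written: SAP 5.2.5 and protocol 9.7.1.5 leave a drug already being taken at first dose in neither the prior nor the concomitant group

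*SAP*

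**What the plan says.** SAP 5.2.5 gives two definitions. For prior: "Prior medications will be defined as medications that stopped prior to the first dose of study drug". For concomitant: "Concomitant medications will be defined as medications that started after the date of the first dose of study drug up to 30 days", counted from the subject's last dose. Protocol 9.7.1.5 agrees on both: "Prior medications will be defined as medications that stopped before the first dose of study drug" and "Concomitant medications will be defined as medications that started after the date of the first dose of study drug", with the same 30-day end. In both documents the summary table, produced on the Full Analysis Set, covers prior and concomitant medications only. Both also provide complete listings; in the SAP, "All medications will be presented in subject data listings".

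The drugs at issue are collected. Under protocol 9.4.8, medication or "therapy administered to the subject during the study (starting at the date of informed consent) will be recorded" on the case report form. The protocol also expects drugs that run across the first dose:

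- Section 9.3.2, on hepatitis B: "Subjects with HBV are eligible, but should be taking appropriate antiviral medication if indicated".
- Section 9.3.1, criterion 14: hormonal contraceptive users must have been "on a stable dose of the same hormonal contraceptive product for at least 4 weeks before dosing and must continue" during the study and for 30 days after stopping study drug.
- Section 9.4.8.2 lets subjects carry on with medications they were already taking for underlying conditions, antiemetics and antidiarrheals among them.

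SAP sections 8 and 9 refer further data-handling conventions and derivation rules to separate documents.

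**The concern.** A medication table is usually read as a description of what subjects were taking while on study drug. Under the written rule it would show drugs finished before treatment and drugs begun after the first-dose date, but not therapy already in place at first dose and continued. That background therapy is what the protocol most plainly anticipates at entry. Safety is a primary objective, and protocol 7.1.1.3 names gastrointestinal toxicity among the possible drug effects, so a reader of the AE tables would want to know how many subjects were already on antiemetics or antidiarrheals. The listings contain that information, but not as counts and percentages.

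**Working it through.** The plan gives no figure to reproduce, so the check is date logic.

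**Inputs** (SAP 5.2.5, same in protocol 9.7.1.5). Let Day 1 be the first-dose date, L the day of the last dose, s the start day of a medication and e its stop day (missing if ongoing). Dates are compared as whole days.

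- Prior: e < 1.
- Concomitant: 1 < s ≤ L + 30.
- Proposed concomitant rule: s ≤ L + 30, and e ≥ 1 or ongoing.

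L = 84 serves as an example only; then L + 30 = 114 and L + 31 = 115.

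| Start | Stop | As written | Proposed rule |
|---|---|---|---|
| Day -30 | Day -5 | prior | prior |
| Day -30 | Day 20 | neither | concomitant |
| Day -30 | ongoing | neither | concomitant |
| Day 1 | Day 1 | neither | concomitant |
| Day 1 | ongoing | neither | concomitant |
| Day 2 | Day 10 | concomitant | concomitant |
| Day 114 | ongoing | concomitant | concomitant |
| Day 115 | ongoing | neither (outside the window, as intended) | neither |

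The gap is therefore every medication with s ≤ 1 that was not stopped before first dose. The result does not depend on L.

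**Hormonal contraceptives as a test case.** Criterion 14 requires a stable dose for at least 4 weeks (28 days) before dosing, so s < 1 and the concomitant rule fails. It also requires use until 30 days after study drug is stopped, so e > 1 and the prior rule fails. A user who complies with the criterion can fall in neither group.

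**Is it repaired elsewhere?** No other section of either document adds a category or convention for medications ongoing at first dose. SAP section 8 defines baseline values but says nothing on medication timing, and then points to the programming specifications.

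**Optional point on adverse events.** SAP 5.6.2 ends treatment emergence 28 days after last dose. Protocol 9.5.1.4.1 collects AEs through the off-treatment visit, put at within 30 days: 30 - 28 = 2 days of collected onsets outside the window. Protocol 9.1.2.4 sets that visit at 30 ± 3 days, that is Day 27 to Day 33 after last dose. If collection follows the actual visit, the difference runs from 0 days (27 is before 28) to 33 - 28 = 5 days.

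**The case against.** The strongest reply is that this is a drafting slip with little practical effect. The protocol discusses continuing entry medications under its heading for permitted concomitant therapy, and one form collects prior and concomitant drugs together, so the intended meaning is fairly clear. Every medication is listed. Baseline medical conditions (SAP 5.2.4) and major protocol deviations (SAP 5.2.3) are summarized separately. The programming specifications may already apply the usual rule.

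Most of this stands, and it keeps the point minor. It does not remove it. The opening of SAP section 5 says that analyses are generated according to the SAP and that deviations are documented in the study report, so a programmer who applied ordinary usage would be departing from the written definition.

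A reader might go further in three ways that the documents do not support.

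- One might infer that data are lost or the safety conclusions distorted. The drugs are recorded and listed, and medication use is not an endpoint.
- One might gauge the size by counting timing patterns or the types of drug that the protocol mentions. Such counts say nothing about subjects. Several of the drug types are conditional permissions, one is very broad, and a simple split into four timing classes still misses a drug started and stopped on Day 1.
- One might treat the 28-day TEAE window as a second error. A TEAE window need not equal the collection period, and protocol 9.7.1.8.2 states no day limit for the SAP to contradict. All AEs are listed.

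**Conclusion.** The concern holds as a minor point that is wrong as written. The two definitions do not meet at the first dose, and a medication started on or before that date and not stopped before first dose belongs to neither group. On a literal reading it is missing from one descriptive table and present in the listings. DLT/MTD determination, the response rate and all other endpoints are unaffected.

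The gap in the wording is certain. The gap in the table is conditional: it assumes that the table is programmed from the SAP text and that the programming specifications do not already override it. The number of subjects affected cannot be derived from the documents and is not estimated. The difference between the 28-day TEAE window and AE collection to about 30 days is an optional alignment, not an error.

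**What to change.** In SAP 5.2.5 and protocol 9.7.1.5, define concomitant medication as any medication taken on or after the date of first dose up to 30 days after last dose, including those started earlier and still ongoing at first dose. The definition of prior can stay. If the protocol is not to be amended again, record the change in SAP section 7. If the programming specifications already use this rule, state it in the SAP text.

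The cost is a short edit in each document. No new data are needed, since medications are recorded from consent. The downside is a longer medication table.

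Optionally, in SAP 5.6.2, align the TEAE window with AE collection or add a sentence saying why 28 days was chosen. A longer window could raise TEAE counts slightly.

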### 5.2.6 Treatment Compliance

Subjects with treatment related protocol deviations will be summarized.

## 5.3 Data Analysis General Considerations

### 5.3.1 Pooling of Centers

Subjects from all centers will be pooled for all analyses.

### 5.3.2 Adjustments for Covariates

Not applicable.

### 5.3.3 Multiple Comparisons/Multiplicity

Not applicable.

### 5.3.4 Examination of Subgroups

No formal subgroup analyses are planned. Exploratory subgroup analyses may be performed as needed.

### 5.3.5 Handling of Missing Data, Drop-outs, and Outliers

In general, missing or incomplete data, including dates, will be treated as missing or incomplete and no data imputation will be applied. Data that are potentially spurious or erroneous will be queried and examined during the review of the study data.

For efficacy data summarized for the FAS for HCC subjects, subjects who start trial therapy and drop out prior to any tumor response assessment for any reason will be considered as nonresponders and will be included in the denominator when calculating the response rate.

Some numerical laboratory data may contain a “<” or “>” or letters, the numerical value will be used for calculation and analysis in tables and figures and the complete character records in listings.

## 5.4 Efficacy Analyses

Efficacy analyses will be based on the FAS for HCC subjects only and/or Response Evaluable Set.

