9.7.1.2 Definitions of Analysis Sets

Analyses will be performed using the following analysis sets:

- **Full Analysis Set**, which will include all subjects who receive at least 1 dose of study drug. This will be the primary analysis set for efficacy evaluations, as well as for demographic and baseline characteristics. The summary of efficacy will be based on this set for HCC subjects.
- **Safety Analysis Set**, which will include all subjects who received at least 1 dose of study drug. This will be the analysis set for all safety evaluations except DLT results.
- **PK Analysis Set**, which will include all subjects who have received at least 1 dose of study drug and have at least 1 evaluable plasma concentrations.
- **Pharmacodynamics Analysis Set**, which will include all subjects who have received at least 1 dose of study drug and have evaluable pharmacodynamic data.

- **PK/Pharmacodynamics Analysis Set**, which will consist of all subjects in the Safety Analysis Set that also have evaluable plasma PK and pharmacodynamic pretreatment assessment and at least 1 posttreatment assessment.
- **Response Evaluable Set**, which will consist of those HCC subjects who have received at least 1 dose of study drug and have measurable disease at baseline and at least 1 postbaseline evaluation.

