9.7.1.6 Efficacy Analyses

The efficacy analyses will be performed at the time of data cutoff for primary analysis.

ORR, response duration, time to response, PFS, and OS will be listed and descriptively summarized as appropriate. All efficacy parameters will be summarized for the Full Analysis Set for HCC subjects. In addition, ORR, duration of response, and time to response will also be summarized for the Response Evaluable Set as appropriate.

ORR will be reported in summary tables.

For response duration and time to response, summary statistics (median Q1, Q3 and range) will be generated on subjects achieving a best overall response of PR or CR (PR + CR). The summary statistics will be generated using Kaplan-Meier estimate.

For PFS, subjects who do not have progression of disease or death information will be treated as right-censored observations at the time of the last response evaluation. The PFS censoring rules will follow the FDA guidance. PFS will be reported in both summary tables and plotted with Kaplan-Meier curve.

For OS, time of death will be censored for subjects who are without death information at the time of OS analysis. OS will be reported in both summary tables and plotted with Kaplan-Meier curve.

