## 5.2 Study Subjects

### 5.2.1 Definitions of Analysis Sets

**Full Analysis Set (FAS)** will include all subjects who received at least 1 dose of study drug. This will be the primary analysis set for demographic and baseline characteristics. Efficacy analysis will be based on FAS for HCC subjects only.

**Safety Analysis Set** will include all subjects who received at least 1 dose of study drug. This will be the analysis set for all safety evaluations except DLT results.

**DLT Analysis Set** will include all subjects in Dose Escalation phase (Part 1) who are evaluable for a DLT. To be evaluable for a DLT, subjects must have completed safety assessments through predose on C2 Day 1 and must have received at least 17 of 21 (approximately 80%) study days within C1, unless due to a DLT. This will be the analysis set for analyzing DLT results only.

**PK Analysis Set** will include all subjects who have received at least 1 dose of study drug and have at least 1 evaluable plasma concentration.

**Pharmacodynamics Analysis Set** will include all subjects who have received at least 1 dose of study drug and have evaluable pharmacodynamic data.

**PK/Pharmacodynamics Analysis Set** will consist of all subjects in the Safety Analysis Set that also have evaluable plasma PK and pharmacodynamic pretreatment assessment and at least 1 post treatment assessment.

**Response Evaluable Set** will consist of those HCC subjects who have received at least 1 dose of study drug and have measurable disease at baseline and at least 1 post-baseline evaluation.

The number (percentage) of subjects enrolled in the study and included in each analysis set will be summarized.

A listing of subjects included in each analysis set will be provided.

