### 5.4.1 Analysis of Efficacy Endpoints Based on Tumor Response

ORR, duration of response (DOR), time to response and PFS will be analyzed on the FAS for HCC subjects and Response Evaluable Set as appropriate.

The exact 95% confidence intervals of ORR will be calculated using Clopper-Pearson method. DOR and time to response will be for subjects who have achieved a best response of CR or PR only. Censoring rules for PFS will follow the FDA guidance and are specified in Table 5. PFS will be reported in both summary tables and plotted with Kaplan-Meier curve.

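### The SAP leaves the primary efficacy set unsettled and adds PFS to the Response Evaluable Set, which by definition omits subjects who die without a post-baseline evaluation

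*SAP*

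**What the plan says.** **Protocol.** Section 9.7.1.2 says of the FAS: "This will be the primary analysis set for efficacy evaluations, as well as for demographic and baseline characteristics". Section 9.7.1.6 says: "All efficacy parameters will be summarized for the Full Analysis Set for HCC subjects". It then adds the evaluable set for three endpoints only: "In addition, ORR, duration of response, and time to response will also be summarized for the Response Evaluable Set as appropriate". PFS is not among them.

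**SAP.** Three places describe the efficacy set, each differently:

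- Section 5.2.1 bases efficacy on the FAS for HCC subjects, but calls the FAS primary only for demographic and baseline characteristics. The protocol's reference to efficacy is gone from that sentence.
- Section 5.4: "Efficacy analyses will be based on the FAS for HCC subjects only and/or Response Evaluable Set".
- Section 5.4.1: "ORR, duration of response (DOR), time to response and PFS will be analyzed on the FAS for HCC subjects and Response Evaluable Set as appropriate".

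SAP 5.2.1 admits to the Response Evaluable Set only HCC subjects who were dosed and who "have measurable disease at baseline and at least 1 post-baseline evaluation". SAP 5.4.2 keeps OS on the FAS (HCC). SAP section 7 records two changes, the DLT analysis set and the restriction of efficacy summaries to HCC subjects. It records neither the *and/or* nor PFS on the evaluable set.

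**The concern.** There are two linked problems.

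The first is hierarchy. The protocol has a clear order: FAS first, evaluable set in addition. The SAP has no sentence that names the primary efficacy set, and the *or* in 5.4 opens a choice that the protocol does not offer. SAP section 5 says that all analyses are to follow the SAP, so a reader cannot simply fall back on the protocol.

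The second is that membership depends on outcome. The first scheduled tumor assessment is in Week 6. A subject who dies before any assessment has had a PFS event, and that same death keeps the subject out of the evaluable set. A PFS curve on that set is therefore short of events before the first scan by construction.

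Part 2 is meant to characterize preliminary antitumor activity (Protocol 9.1.1.2), and efficacy is one of the inputs for judging QD against BID (Protocol 9.7.2, SAP section 4). PFS and OS could also end up on different populations in the same report.

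**Working it through.** **1. The plan's own figures.** SAP 5.4.1 specifies Clopper-Pearson intervals. For 8 responders of 40, SAP Table 4 gives 0.091 to 0.356, and the exact calculation agrees. Ten of the 11 rows reproduce. In the 4/40 row the upper limit is printed as 0.234 and computes to 0.237, which is a separate matter. The missed-assessment window in SAP Table 5 also reproduces: (6+1) × 2 × 7 - 1 = 97 days.

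**2. The same subject in the two sets.** Take an HCC subject with a baseline scan who dies in week 4, with no post-baseline evaluation and no new anticancer treatment.

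- PFS on the FAS: an event at the date of death (SAP Table 5 and the 97-day rule below it).
- ORR on the FAS: a nonresponder kept in the denominator (SAP 5.3.5).
- Evaluable set: absent, because the entry condition in SAP 5.2.1 is not met.

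Now take a subject with clinical progression, no scan and no death. SAP Table 5 recognizes only radiologic progression and death as events, so this subject is not a PFS event in the FAS either. With no post-baseline assessment, censoring falls in effect at the start, and dropping the subject hardly moves the Kaplan-Meier curve. The PFS distortion therefore comes from early deaths.

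**3. Size for PFS.** Let f be the fraction of the FAS that dies before week 6 without an evaluation, and ignore other exclusions. The number still event-free at any later time t is the same in both sets, but the denominators are N and N(1-f). So for t of 6 weeks or more:

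S_RES(t) = S_FAS(t) / (1-f)

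The documents give no value for f or for PFS after week 6, so both are assumed. The illustration takes all events before week 6 to be unscanned deaths, followed by exponential PFS with residual median M = 12.2 weeks, so λ = ln 2 / 12.2.

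- 12-week PFS, evaluable set: exp(-6λ) = 71.1%. FAS: (1-f) × 71.1%.
- Median, evaluable set: 6 + 12.2 = 18.2 weeks. FAS: 6 + ln((1-f)/0.5)/λ.

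| assumed f | 12-week PFS, FAS | 12-week PFS, evaluable | median, FAS (weeks) | median, evaluable (weeks) |
|---|---|---|---|---|
| 5% | 67.6% | 71.1% | 17.3 | 18.2 |
| 10% | 64.0% | 71.1% | 16.3 | 18.2 |
| 15% | 60.4% | 71.1% | 15.3 | 18.2 |
| 20% | 56.9% | 71.1% | 14.3 | 18.2 |

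With f held at 10% and M varied from 6 to 24 weeks, the evaluable-set median is longer by 0.9 to 3.6 weeks.

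**4. Size for ORR.** With x responders and d subjects lost before any evaluation, ORR moves from x/40 to x/(40-d). For x = 8, FAS ORR is 20.0% (9.1 to 35.6).

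| assumed loss | evaluable-set ORR (exact 95% CI) |
|---|---|
| 4 of 40 (10%) | 8/36 = 22.2% (10.1 to 39.2) |
| 6 of 40 (15%) | 8/34 = 23.5% (10.7 to 41.2) |
| 8 of 40 (20%) | 8/32 = 25.0% (11.5 to 43.4) |

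**5. The other endpoints.** Duration of response and time to response are computed in responders only, so losing subjects who were never evaluated does not change them. OS is on the FAS and is unaffected.

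**The case against.** The strongest reply is that one loose sentence is being read against the rest of the plan. SAP 5.2.1 bases efficacy on the FAS, 5.4.1 joins the two sets with *and*, 5.3.5 keeps early drop-outs in the FAS denominator, and the SAP is written to the protocol version that requires every efficacy parameter on the FAS. Efficacy is secondary and descriptive in a Phase 1 study, so no test, threshold or power figure depends on the set. Counts and listings for each set are already planned.

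Most of this stands, and it rules out several stronger readings that a reader might infer:

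- *That the SAP makes the evaluable set the basis of efficacy.* It permits this through 5.4 but does not require it, and 5.2.1 points the other way.
- *That every death before the first scheduled scan is excluded.* The entry condition does not define an evaluation as a scan, although a tumor assessment is the natural meaning. Scans may be done earlier if clinically indicated. A subject scanned and then dying before Week 6 stays in.
- *That early clinical progressions are PFS events lost from the set.* SAP Table 5 does not count them. Protocol 9.5.1.2.1 also asks for a scan near C3 Day 1 after early discontinuation, so many of these subjects would stay in the set.
- *That ORR on the evaluable set is itself a fault.* Protocol 9.7.1.6 allows it as an additional summary.

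The reply does not answer the addition of PFS. That goes beyond the protocol, is not logged, and applies to a time-to-event endpoint a set whose entry rule removes some of its earliest events. A scan requested near C3 Day 1 cannot recover subjects who have already died.

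**Conclusion.** The point holds as an inconsistency within the SAP and a departure from the protocol, with one analysis that is biased by its own definition: PFS on the Response Evaluable Set. The direction is certain wherever any subject dies without an evaluation, because later PFS is then raised by the factor 1/(1-f). The amount is not known. It is 1.05 at f = 5%, 1.11 at 10% and 1.25 at 20%, and the shift in the median depends further on the assumed PFS after week 6. These figures rest on assumed rates, on reading the required evaluation as a tumor assessment, and on the exclusions being early deaths.

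The higher ORR on the evaluable set is acceptable only as a supportive figure beside the FAS result. The consequence is confined to descriptive reporting of secondary endpoints, but the correction should be made before database lock because it restores the protocol at almost no cost.

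**What to change.** Amend the SAP as follows:

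- In 5.2.1, 5.4 and 5.4.1, state that the FAS for HCC subjects is the primary set for all efficacy endpoints, and replace the *and/or* in 5.4 accordingly.
- In 5.4.1, delete PFS from the endpoints analyzed on the Response Evaluable Set. Keep that set as supportive for ORR, duration of response and time to response, as in Protocol 9.7.1.6.
- Give the reasons for exclusion from the Response Evaluable Set beside the set counts that 5.2.1 already plans. It would also help to say there that the required evaluation is a tumor assessment, if that is what is meant.

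The cost is SAP wording and one fewer PFS table. No new data are needed. The PFS discrepancy between the sets disappears. The ORR difference remains visible, but in a table labelled as supportive.
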